### 9.1.1 *Inclusion criteria*

Following users will be included in the study:

- Online consent form filled out
- Has been fitted with at least one Ponto Sound Processor

### 9.1.2 *Exclusion criteria*

[figure not shown]
There are no exclusion criteria for this study.

### 9.1.3 *Number of subjects*

The aim is to recruit in total approx. 1000 subject. The subjects will be split into sub-groups based on which sound processor they are using.

## 9.2 Study flow

Primarily out-reach will be made through an email. The email will contain overall information about the study and a link to the study landing page. In addition, posts might be made in social media or at Oticon Medical US website with information and a link to the same landing page. On the landing page the participants can get more information about the survey and also provide their informed consent. Following consent, the users will get access to the survey that should be completed within one month. To maximize data collection, e-mail and/or text message reminders to complete the survey will be 7 days after the initial email and 5 days prior to the survey completion deadline. In Figure 3 an overview of the study flow is visualized.

**Figure 3** Scematic overview of the flow of the study

	Title BC112 Cross-sectional evaluation of the subjective performance and satisfaction with Ponto sound processors	Document no Doc-00115596	Revision 1	Page 11(17)
---	---	------------------------------------	----------------------	-----------------------

## 9.2.1 Survey

The study will consist of an online survey distributed to the subjects. The survey consists of two parts:

1. Overall information about the subject and the device
2. A validated questionnaire focusing on subjective performance using a hearing device. For adult participants the questionnaire IOI-HA will be used.

### 9.2.1.1 Part 1 Overall information

Following overall information will be gathered from the participants:

- Gender
- Age
- Usage of device
- Unilateral or bilateral user
- Softband or Abutment fitting
- Time of fitting (for how long they have used the device)

### 9.2.1.2 Part 2 International Outcome Inventory Hearing Aids (IOI-HA)

The IOI-HA is a short questionnaire with generally applicable items used as self-assessment of hearing aid fitting outcomes. The questionnaire consists of seven items: daily use, benefit, residual activity limitation, satisfaction, residual participation restrictions, impact on other and quality of life. Each item has five response choices proceeding from worst to best. Analysis of the results can be done per item or total score. The items can be grouped in two subscales: Factor 1 (daily use, benefit, satisfaction and quality of life) and Factor 2: (residual activity limitation, residual participation restrictions and impact on others) [3].

## 10 MONITORING

Due to the nature of this study, with users reporting data directly into the electronic system, monitoring is not applicable.

## 11 STATISTICAL DESIGN AND ANALYSIS

The results of the IOI-HA (ranging from 1-5, 1=worst and 5= best) will be analyzed and presented using descriptive statistics. The values of the Overall, Factor 1, Factor 2 and per item IOI-HA score will be given as Mean, standard deviation (SD), Median, Minimum and Maximum.

### 11.1 Sample size

The user database currently consists of approx. 3000 users and we expect an initial response-rate of 50%, i.e. that approximately half of the users will respond to the survey invite. As the database continuously increases and outreach through social media and website also is planned additional outreach can be made to fulfill the sample size estimated below.

The IOI-HA have been used for many studies on different number of subjects. The original paper the sample size was 172 [3] and the for the online validation [4] the sample size was 53. However, the IOI-HA has also been used for bigger populations, in [5] the IOI-HA was used on 1649 subjects. For the two studies [3] and [4] the response rate were high and reported drop-out rates were 20% and 34%, respectively. Drop-out is in

	Title BC112 Cross-sectional evaluation of the subjective performance and satisfaction with Ponto sound processors	Document no Doc-00115596	Revision 1	Page 12(17)
---	---	------------------------------------	----------------------	-----------------------

this study defined as the participants not finalizing the survey after filling out the digital consent form. Drop-out rate for this study is expected to be low based on previous reported literature and as the study only consist of one assessment (i.e. the subject filling out one survey at a single point of time). The drop-out rate is estimated to a 30%, aiming for answers from in total 1000 subjects, with minimum 50 subjects from each sub-group 1, 2 and 3.

## 11.2 Subgroups for analysis

Subgroup primary endpoint analysis will be made based on the type of Ponto sound processor. The following subgroups will be analysed:

- Subgroup 1: Ponto, Ponto Pro and Ponto Plus (Ponto, Ponto Pro, Ponto Pro Power, Ponto Plus and Ponto Plus Power)
- Subgroup 2: Ponto 3 SuperPower
- Subgroup 3: Ponto 3 (Ponto 3, Ponto 3 Power)
- Subgroup 4: Ponto 4
- Subgroup 5: Ponto 5 Mini
- Subgroup 6: Ponto 5 SuperPower

## 11.3 Missing data handling

No imputations or estimations will be made to replace missing data.

## 11.4 Timing for data analysis

Data analyses will be performed in three steps. First data analysis will focus on subgroup 1-3. Second data analysis will focus on subgroup 4-5. Third analysis will focus on Subgroup 6. Out-reach to the users will be made according to timing of the analysis, also in three steps. Additional outreaches can be performed to increase the number of participants.

Data cleaning and database lock of the applicable data will be performed before each of the three data analysis.

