### 8.2 Secondary Objective(s)

Secondary objective(s)	Corresponding primary endpoint/outcome variable(s)	Section
A. Evaluate the subjectively assessed performance and satisfaction with Oticon Medical's Ponto sound processors	1. Factor 1 IOI-HA score 2. Factor 2 IOI-HA score 3. Per item IOI-HA score	9.2.1.2
B. Evaluate non-usage among patients fitted with a Ponto sound processor	1. Percentage of users fitted with a Ponto sound processor that have stopped using the Ponto sound processor and is unaided	
C. Evaluate Ponto sound processor upgrade rate	1. Percentage of users who have been refitted with a Ponto sound processor	

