## 9.1 Subjects

The population for this study will be users of Ponto Sound Processors in the US. User who are a part of Oticon Medical's US user database where the users are signing up in relation to being fitted with a Ponto Sound Processor will be approached through email out-reach. When signing up for the database the users give their consent for being contacted by Oticon Medical. In addition, out-reach through social media and Oticon Medical US website will be considered to increase numbers of subjects. In all both cases, study awareness and enrollment of the participants for this study will occur after being fitted with one or two Ponto sound processor.

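### Non-usage (B) and 'upgrade rate' (C) in 8.2 have no time at risk, so any overall percentage mixes behaviour with time since fitting and respondent mix

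*Combined protocol and SAP*

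**What the plan says.** All places are in the combined protocol and SAP.

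- **Endpoints.** Section 8.2 defines B as "Percentage of users fitted with a Ponto sound processor that have stopped using the Ponto sound processor and is unaided". Objective C is to "Evaluate Ponto sound processor upgrade rate", and its endpoint is "Percentage of users who have been refitted with a Ponto sound processor". Neither has a window, years at risk or a stated denominator. C does not appear in the synopsis.
- **Planned analysis.** Section 11 covers the questionnaire only: "The values of the Overall, Factor 1, Factor 2 and per item IOI-HA score will be given as Mean, standard deviation (SD"), followed by median, minimum and maximum. Section 11.2 limits the subgroup work: "Subgroup primary endpoint analysis will be made based on the type of Ponto sound processor". No analysis of B or C is described.
- **How the sample is built.** Section 9.1.3 groups people by the processor they are using. Section 11.4 takes subgroups 1-3 first, then 4-5, then 6, and adds "Out-reach to the users will be made according to timing of the analysis, also in three steps". Additional outreach is permitted. The only minimum counts are in section 11.1: "with minimum 50 subjects from each sub-group 1, 2 and 3".
- **Who is in the frame.** Section 9.1 describes a US user database where "the users are signing up in relation to being fitted with a Ponto Sound Processor". Section 11.1 says that it keeps growing. Social media and the sponsor's website may add respondents.
- **What is collected.** Part 1 of the survey (9.2.1.1) includes device usage and a time-of-fitting item, explained as how long the device has been used. It lists no previous processor and no refitting item.

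**The concern.** The proportion who have ever stopped, or ever been refitted, tends to grow with the time a person has had to do so. Section 6 states an interest in long-term use, yet B puts someone fitted last month in the same denominator as someone fitted many years ago.

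C has a second difficulty. A refit to a newer family moves a person into a later subgroup, and outreach follows the subgroups. Sampling by current processor is therefore, in part, sampling on the outcome.

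At stake is interpretation. A reader of the final report could take the figures as how often Ponto users stop or upgrade, when a different yield from the three steps would have given different figures with no change in user behaviour. The name 'upgrade rate' invites that reading.

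**Working it through.** **1. The plan's own figure.** Section 11.1 gives about 3000 users, a 50% response and a 30% drop-out after consent:

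3000 × 0.50 × (1 − 0.30) = 1050 completers.

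This is consistent with the aim of about 1000. Conversely, 1000 / 0.70 ≈ 1429 consents are needed and 1500 are expected. There is no error here, but no figure or precision target is given for B or C.

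**2. What fixes the mix.** The minimums total 3 × 50 = 150, or 15% of 1000. Step 1 could supply anything from 15% of respondents upwards, and nothing is set for subgroups 4-6.

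**3. Sensitivity of B to mix.** Every input in steps 3 and 4 is an assumption. Take 7, 2 and 0.5 years since fitting for people reached in outreach steps 1, 2 and 3, and one constant stopping hazard h for everybody:

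overall % = Σ share × [1 − exp(−h × years)]

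For h = 0.02 the three terms are 13.1%, 3.9% and 1.0%. With shares 70/20/10: 0.7 × 13.1 + 0.2 × 3.9 + 0.1 × 1.0 ≈ 10.0%.

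| Hazard per year | 70/20/10 | Even thirds | 15/50/35 |
|---|---|---|---|
| 1% | 5.2% | 3.1% | 2.2% |
| 2% | 10.0% | 6.0% | 4.3% |
| 4% | 18.8% | 11.4% | 8.2% |

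Down a column the figure follows true stopping. Along a row it follows mix alone. A hazard of 1% with the first mix (5.2%) gives a higher figure than a hazard of 2% with the third (4.3%).

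**4. Sensitivity of C to mix.** Overall % = Σ share × share refitted in that step. For example, 0.7 × 10 + 0.2 × 50 + 0.1 × 70 = 24.0%.

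| Assumed refitted, steps 1/2/3 | 70/20/10 | Even thirds | 15/50/35 |
|---|---|---|---|
| 10/50/70% | 24.0% | 43.3% | 51.0% |
| 20/40/50% | 27.0% | 36.7% | 40.5% |
| 30/30/30% | 30.0% | 30.0% | 30.0% |

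The last row shows the condition: if refit shares do not differ between steps, mix has no effect.

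**5. Comparison with sampling error.** The 95% half-width is 1.96 × √(p(1 − p)/n). At n = 1000 it is 1.9 points at 10% and 2.8 points at 30%. Under the unequal assumptions above, mix can outweigh sampling error.

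**6. Data sources.** B can probably be drawn from the usage item. C has no stated source in Part 1. For a refitted user, the time-of-fitting item may give only the time on the current processor, which is not the time at risk of a first upgrade.

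**The case against.** Much of the case on the other side stands, and it limits the point.

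- **B is a proper cross-sectional quantity.** A reader might infer that B and C show the outreach mix instead of real behaviour. They do not: B is a point prevalence, and the hazard columns above show that it responds to true stopping. The problem is confounding.
- **Staging alone does not bias.** The three steps together cover all six subgroups, which include every family in section 5.1. If the whole database is invited and responds evenly, the database mix comes back. What remains is that nothing in the plan secures even coverage, response or top-up.
- **Processor is only a partial proxy for upgrading.** A reader might infer that anyone surveyed on a Ponto 3 in the first step counts as not refitted. Section 8.2 does not say so. That person may have moved from a Ponto, Ponto Pro or Ponto Plus and would then count as refitted.
- **Pooling is not stated.** Section 11.4 describes three locks and three analyses, and the plan does not say whether B and C will be combined across them. The point concerns any overall figure that is reported.
- **Double counting is speculative.** No rule bars a second response after an upgrade. It would, however, need an upgrade between steps and a second consent within a 10-month study, and subject numbers are linked to email addresses.
- **Time of fitting is already collected.** B could be tabulated by reported duration without new data. No planned analysis does so.

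**Conclusion.** The concern holds in this form. B and C have no time at risk and no planned analysis by time since fitting. An overall percentage from this sample therefore confounds stopping or upgrading with time since fitting and respondent mix whenever coverage, response or top-up differs between steps. C is the weaker of the two: it is called a rate, its data source is not listed, and the variable that drives outreach is partly its outcome.

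The shifts shown, from 10.0% to 4.3% for B at 2% per year and from 24% to 51% (milder case 27% to 40.5%) for C, rest wholly on assumed rates, years and mixes. They show sensitivity and are not estimates of bias. Both endpoints are secondary and descriptive, and the point does not touch the primary endpoint. The change is worth making because it is cheap, but the study does not depend on it.

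**What to change.** In sections 8.2 and 11:

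1. Report B and C by time since first Ponto fitting, for example under 1, 1-3, 3-5 and over 5 years, with numerator and denominator in each band.
2. In Part 1, word the time-of-fitting item so that it captures first Ponto fitting as well as the current device, and add an item on refitting so that C has a source.
3. Describe any overall figure as the percentage among respondents, and do not call it a rate.
4. Count each person once in any overall figure, using the email link in the EDC system.

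Weighting to the processor mix of the database is not part of this recommendation. Respondents from social media or the website may lie outside the database, and people who have stopped have no clear place in a grouping by processor in use.

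**Cost:** one or two survey items, one extra table and a few sentences of text. Some bands will be small: with 50 people and 10% non-usage the 95% half-width is about 8.3 points, so counts should be shown beside the percentages.

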# 12 DATA MANAGEMENT

All data collected and processed concerning the subjects participating in the study are protected under the Regulation (EU) 2016/679 (GDPR) and Health Insurance Portability and Accountability Act (HIPAA) and will be handled accordingly. Further, professional secrecy regarding subject information and data applies to all involved personnel.

The data from the online survey will be recorded into an electronic data capture (EDC) system. In the EDC system all subjects enrolled in the study will be assigned a Subject Identification Number with a link to their personal identification (email address). The personal identification information will be used for sending out emails with the surveys. The subject can at any time ask to get their personal identification information removed. The access to the EDC system is restricted and will be limited to a couple of users with administrative rights.

	Title BC112 Cross-sectional evaluation of the subjective performance and satisfaction with Ponto sound processors	Document no Doc-00115596	Revision 1	Page 13(17)
---	---	------------------------------------	----------------------	-----------------------

### 12.1 **Data Management Plan**

Data management-related activities, e.g. data cleaning, will be performed by the data manager. Once all data has been captured, reviewed and declared clean the database will be locked before any data analysis.

## 13 AMENDMENTS TO THE CIP

Substantial amendments should be approved by the IRB as applicable, before incorporated. In addition, substantial amendments to the Study Information and Consent Form and/or other applicable documents previously approved by the IRB must be approved by the IRB before they will come into effect. For non-substantial amendments, local regulations regarding notifications to IRB should be followed.

If study deemed exempt IRB approval amendments to this protocol and accompanying material will be made without notifying the IRB. Only if amendments to the protocol are made that might affect the exemption, IRB will be notified.

## 14 DEVIATIONS FROM THE PROTOCOL

A deviation is an intentional or unintentional failure to follow the requirements of the protocol. Every effort should be made to comply with the requirements of the protocol. If deviations occur a record should be made in a deviation log. The implications of the deviation must be reviewed and discussed as soon as possible after detection. All protocol deviations must be documented stating the reason, date, the action(s) taken, and the impact for the subjects and/or the study. At the end of the study, protocol deviations will be categorized as minor or major and their consequence on analysis populations will be determined.

## 15 DEVICE ACCOUNTABILITY

Not applicable. Participants will evaluate their own devices.

## 16 STATEMENTS OF COMPLIANCE

Applicable parts of ISO 14155, Regulation (EU) 2017/745 (MDR) as specified in this CIP will be adhered to. The CIP, the Subject Information, the Online Informed Consent Form and other required documents will be submitted to an Institutional Review Board (IRB). Documentation will be reviewed and approved, or deemed exempt, in writing, by IRB before enrollment of subjects into the study can be initiated. Any additional requirements imposed by IRB shall be followed.

## 17 INFORMED CONSENT

Prior to providing the subjects with the survey they will be provided with written information in an electronic form. The information will contain detailed information about the study including the purpose, procedures and how the subject's data will be handled in the study. The information will contain contact details to sponsor in case of any questions. Subject consent will be obtained electronically and documented. No study-specific data collection will occur prior to subject consent.

## 18 ADVERSE EVENTS, ADVERSE DEVICE EFFECTS AND DEVICE DEFICIENCIES

As the study has patient reported outcomes with focus on subjective performance and satisfaction, there will be no adverse events, adverse device effects, or device deficiencies collected.

## 19 VULNERABLE POPULATION (IF APPLICABLE)

No vulnerable population to be included in the study.

## 20 SUSPENSION OR EARLY TERMINATION OF THE CLINICAL STUDY

The sponsor may at any time terminate the study. If the study is terminated prematurely the concerned IRB will be informed promptly in writing by the sponsor.

## 21 PUBLICATION POLICY

A description of this study will be available, throughout the whole duration and onwards, on [www.ClinicalTrials.gov](http://www.ClinicalTrials.gov).

When the clinical Study is completed, even if prematurely terminated, a final report will be compiled, and the results will be made publicly available. The results obtained in the study might be submitted for publication in scientific journals by the sponsor. Privacy and confidentiality of information about each subject will be preserved in any reports and any publications of the clinical Study data.

## 23 APPENDICES

### Appendix 1. Part number for devices included in the study

Style/side Colour	Ponto		Ponto Pro		Ponto Pro Power	
	Left	Right	Left	Right	Left	Right
White Silver	130-00-113-00	130-00-123-00	130-00-213-00	130-00-223-00	M50903	M50902
Chroma Beige	130-00-110-00	130-00-120-00	130-00-210-00	130-00-220-00	M50875	M50874
Mocca Brown	130-00-111-00	130-00-121-00	130-00-211-00	130-00-221-00	M50873	M50872
Diamond Black	130-00-112-00	130-00-122-00	130-00-212-00	130-00-222-00	M50677	M50676

Style/side Colour	Ponto Plus		Ponto Plus Power	
	Left	Right	Left	Right
White Silver	M51706	M51707	M51736	M51737
Chroma Beige	M51704	M51705	M51734	M51735
Mocca Brown	M51702	M51703	M51732	M51733
Diamond Black	M51700	M51701	M51730	M51730

Style/side Colour	Ponto 3		Ponto 3 Power		Ponto 3 SuperPower	
	Left	Right	Left	Right	Left	Right
Pure White	M52630	M52631	M52644	M52645	M52658	M52659
White Silver	M52626	M52627	M52640	M52641	M52654	M52655
Chroma Beige	M52624	M52625	M52638	M52639	M52652	M52653
Mocca Brown	M52622	M52623	M52636	M52637	M52650	M52651
Steel Grey	M52628	M52629	M52642	M52643	M52656	M52657
Diamond Black	M52620	M52621	M52634	M52635	M52648	M52648

Style Colour	Ponto 4		Ponto 5		Ponto 5 SuperPower	
	Left	Right	Left	Right	Left	Right
CBE Chroma Beige CO90	186777		223156		223162	
TC Terracotta CO94	186778		223157		223163	
SIL Silver CO44	186779		223155		223161	
STG Steel Grey CO92	186780		223159		223165	
CNB Chestnut Brown CO93	186781		223158		223164	
DBL Diamond Black CO63	867821		223160		223166	

## Appendix 2 The International Outcome Inventory of hearing aids

INTERNATIONAL OUTCOME INVENTORY – HEARING AIDS  
(IOI-HA)

1. Think about how much you used your present hearing aid(s) over the past two weeks. On an average day, how many hours did you use the hearing aid(s)?

none	less than 1 hours a day	1 to 4 hours a day	4 to 8 hours a day	more than 8 hours a day
				

2. Think about the situation where you most wanted to hear better, before you got your present hearing aid(s). Over the past two weeks, how much has the hearing aid helped in that situation?

helped not at all	helped slightly	helped moderately	helped quite a lot	helped very much
				

3. Think again about the situation where you most wanted to hear better. When you use your present hearing aid(s), how much difficulty do you **STILL** have in that situation?

very much difficulty	quite a lot of difficulty	moderate difficulty	slight difficulty	no difficulty
				

4. Considering everything, do you think your present hearing aid(s) is worth the trouble?

not at all worth it	slightly worth it	moderately worth it	quite a lot worth it	very much worth it
				

5. Over the past two weeks, with your present hearing aid(s), how much have your hearing difficulties affected the things you can do?

affected very much	affected quite a lot	affected moderately	affected slightly	affected not at all
				

6. Over the past two weeks, with your present hearing aid(s), how much do you think other people were bothered by your hearing difficulties?

bothered very much	bothered quite a lot	bothered moderately	bothered slightly	bothered not at all
				

7. Considering everything, how much has your present hearing aid(s) changed your enjoyment of life?

worse	no change	slightly better	quite a lot better	very much better

